### **Prior/Concurrent Clinical Study Experience:**

10. Previous administration with an investigational product (drug or vaccine) within 30 days (or as determined by the local requirement) or 5 half-lives preceding the first dose of study intervention used in this study (whichever is longer). Participants who have participated in previous clinical trials with nirmatrelvir may be eligible to participate in this study as long as they meet all other criteria.

### **Diagnostic Assessments:**

11. A positive urine drug test.
12. Screening supine BP  $\geq 140$  mm Hg (systolic) or  $\geq 90$  mm Hg (diastolic), following at least 5 minutes of supine rest. If BP is  $\geq 140$  mm Hg (systolic) or  $\geq 90$  mm Hg (diastolic), the BP should be repeated 2 more times and the average of the 3 BP values should be used to determine the participant's eligibility.
13. Standard 12-lead ECG (single) that demonstrates clinically relevant abnormalities that may affect participant safety or interpretation of study results (eg, baseline QTcF interval  $>450$  msec, complete LBBB, signs of an acute, old or age indeterminate myocardial infarction, ST-T interval changes suggestive of myocardial ischemia, second- or third-degree AV block, or serious bradyarrhythmias or tachyarrhythmias). If the baseline uncorrected QT interval is  $>450$  msec, this interval should be

rate-corrected using the Fridericia method and the resulting QTcF should be used for decision making and reporting. If QTcF exceeds 450 msec, or QRS exceeds 120 msec, the ECG should be repeated 2 more times and the average of the 3 QTcF or QRS values should be used to determine the participant's eligibility. Computer-interpreted ECGs should be overread by a physician experienced in reading ECGs before excluding a participant.

14. Participants with **ANY** of the following abnormalities in clinical laboratory tests at Screening, as assessed by the study-specific laboratory and confirmed by a single repeat test, if deemed necessary:
  - AST **or** ALT level  $>1.5 \times$  ULN;
  - Total bilirubin level  $\geq 1.5 \times$  ULN; participants with a history of Gilbert's syndrome may have direct bilirubin measured and would be eligible for this study provided the direct bilirubin level is  $\leq$ ULN.
  - eGFR  $<60$  mL/min/1.73 m^2 based on the CKD-EPI equation.

#### **Other Exclusion Criteria:**

15. History of alcohol abuse or binge drinking and/or any other illicit drug use or dependence within 6 months of Screening. Binge drinking is defined as a pattern of 5 (male) and 4 (female) or more alcoholic drinks in about 2 hours. As a general rule, alcohol intake should not exceed 14 units per week (1 unit = 8 ounces (240 mL) beer, 1 ounce (30 mL) of 40% spirit, 3 ounces (90 mL) of wine).
16. Use of tobacco or nicotine-containing products in excess of the equivalents of 5 cigarettes per day or 2 chews of tobacco per day.
17. Blood donation (excluding plasma donations) of approximately 1 pint (500 mL) or more within 60 days prior to dosing.
18. History of sensitivity to heparin, heparin-induced thrombocytopenia.
19. Unwilling or unable to comply with the criteria in the **Lifestyle Considerations** section of this protocol.
20. Investigator site staff directly involved in the conduct of the study and their family members, site staff otherwise supervised by the investigator, and sponsor and sponsor delegate employees directly involved in the conduct of the study and their family members.
21. History of sensitivity reactions to nirmatrelvir, ritonavir, or any of the formulation components of nirmatrelvir, or ritonavir.

22. Pregnant or breastfeeding women.

### **5.3. Lifestyle Considerations**

#### **5.3.1. Contraception**

The investigator or their designee, in consultation with the participant, will confirm that the participant is utilizing an appropriate method of contraception for the individual participant and their partner(s) from the permitted list of contraception methods (see [Appendix 4 Section 10.4.4](#)) and will confirm that the participant has been instructed in its consistent and correct use. At time points indicated in [SoA](#), the investigator or designee will inform the participant of the need to use highly effective contraception consistently and correctly and document the conversation and the participant's affirmation in the participant's chart. Participants need to affirm their consistent and correct use of at least 1 of the selected methods of contraception, considering that their risk for pregnancy may have changed since the last visit.

In addition, the investigator or designee will instruct the participant to call immediately if the selected contraception method is discontinued and document the requirement to use an alternate protocol-specified method, including if the participant will no longer use abstinence as the selected contraception method, or if pregnancy is known or suspected in the participant or partner.

#### **5.3.2. Meals and Dietary Restrictions**

- Participants must abstain from all food and drink (except water) at least 4 hours prior to any safety laboratory evaluations and 10 hours prior to the collection of the predose PK sample on Day 1 of each Period.
- Water is permitted until 1 hour prior to study intervention administration. Water may be consumed without restriction beginning 1 hour after nirmatrelvir/ritonavir dosing. Noncaffeinated drinks (except red wine, grapefruit or grapefruit-related citrus fruit juices—see below) may be consumed with meals and the evening snack.
- Lunch will be provided approximately 4 hours after nirmatrelvir/ritonavir dosing.
- Dinner will be provided approximately 9 to 10 hours after nirmatrelvir/ritonavir dosing.
- An evening snack may be permitted.
- Participants will refrain from consuming red wine, grapefruit, or grapefruit-related citrus fruits (eg, Seville oranges, pomelos, fruit juices) from 7 days prior to the first dose of study intervention until collection of the final PK blood sample.

- While participants are confined, their total daily nutritional composition should be approximately 55% carbohydrate, 30% fat, and 15% protein. The daily caloric intake per participant should not exceed approximately 3200 kcal.

#### **5.3.3. Caffeine, Alcohol, and Tobacco**

- Participants will abstain from caffeine-containing products for 24 hours prior to the start of dosing until collection of the final PK sample.
- Participants will abstain from alcohol for 24 hours prior to admission (or as specified above for red wine) to the CRU and continue abstaining from alcohol until collection of the final PK sample. Participants may undergo an alcohol breath test or blood alcohol test at the discretion of the investigator.
- Participants will abstain from the use of tobacco or nicotine-containing products for 24 hours prior to dosing and during confinement in the CRU.

#### **5.3.4. Activity**

- Participants will abstain from strenuous exercise (eg, heavy lifting, weight training, calisthenics, aerobics) for at least 48 hours prior to each blood collection for clinical laboratory tests. Walking at a normal pace will be permitted;
- In order to standardize the conditions on PK sampling days, participants will be required to refrain from lying down (except when required for BP, PR, and ECG measurements), eating, and drinking beverages other than water during the first 4 hours after nirmatrelvir/ritonavir dosing;
- Participants may be confined to the procedure room for the first 4 hours after dosing on Day 1, except to use the bathroom. After this, participants may be ambulatory but should not engage in strenuous activities.

#### **5.4. Screen Failures**

Screen failures are defined as participants who consent to participate in the clinical study but are not subsequently enrolled in the study. Screen failure data are collected and remain as source and are not reported on the CRF.

Individuals who do not meet the criteria for participation in this study (screen failure) may be rescreened.

### **6. STUDY INTERVENTION(S) AND CONCOMITANT THERAPY**

Study interventions are all prespecified investigational and noninvestigational medicinal products/auxiliary medicinal products, medical devices, and other interventions (eg, surgical and behavioral) intended to be administered to the study participants during the study conduct.

For the purposes of this protocol, study intervention refers to nirmatrelvir and ritonavir.

### 6.1. Study Intervention(s) Administered

For this study, the study interventions are the nirmatrelvir/ritonavir FDC tablets Test formulation 1 (Test 1), nirmatrelvir/ritonavir FDC tablets Test formulation 2 (Test 2), nirmatrelvir/ritonavir FDC tablets Test formulation 3 (Test 3), nirmatrelvir/ritonavir FDC tablets Test formulation 4 (Test 4) and a commercial tablet formulation of nirmatrelvir (Reference formulation), and will be supplied by Pfizer.

Commercially available 100 mg ritonavir tablets will be supplied by the PCRU.

Study Intervention(s)						
Intervention Name	Nirmatrelvir	Ritonavir	Nirmatrelvir/ ritonavir	Nirmatrelvir/ ritonavir	Nirmatrelvir/ ritonavir	Nirmatrelvir/ ritonavir
Arm Name (group of participants receiving a specific treatment or no treatment)	nirmatrelvir/ ritonavir commercial tablets	nirmatrelvir/ ritonavir commercial tablets	nirmatrelvir/ ritonavir FDC tablets Test formulation 1	nirmatrelvir/ ritonavir FDC tablets Test formulation 2	nirmatrelvir/ ritonavir FDC tablets Test formulation 3	nirmatrelvir/ ritonavir FDC tablets Test formulation 4
Unit Dose Strength(s)	150 mg	100 mg	150/50 mg	150/50 mg	150/50 mg	100/33.3 mg
Route of Administration	Oral	Oral	Oral	Oral	Oral	Oral
Use	Reference	Reference	Test 1	Test 2	Test 3	Test 4
IMP or NIMP/AxMP	IMP	NIMP	IMP	IMP	IMP	IMP

Study Arm(s)					
Arm Title	Nirmatrelvir/ ritonavir commercial tablets	Nirmatrelvir/ ritonavir FDC tablets Test formulation 1	Nirmatrelvir/ ritonavir FDC tablets Test formulation 2	Nirmatrelvir/ ritonavir FDC tablets Test formulation 3	Nirmatrelvir/ ritonavir FDC tablets Test formulation 4
Arm Type	Reference	Experimental	Experimental	Experimental	Experimental
Arm Description	Single oral dose of nirmatrelvir/ ritonavir 300 (2 x 150)/100 mg commercial tablets under fasted conditions (Reference)	Single oral dose of nirmatrelvir/ ritonavir 300/100 mg (2 x 150/50 mg) FDC tablets Test formulation 1 (low disintegrant) under fasted conditions (Test 1)	Single oral dose of nirmatrelvir/ ritonavir 300/100 mg (2 x 150/50 mg) FDC tablets Test formulation 2 (high disintegrant) under fasted conditions (Test 2)	Single oral dose of nirmatrelvir/ ritonavir 300/100 mg (2 x 150/50 mg) FDC tablets Test formulation 3 (high drug loading) under fasted conditions (Test 3)	Single oral dose of nirmatrelvir/ ritonavir 300/100 mg (3 x 100/33.3 mg) FDC tablets Test formulation 4 under fasted conditions (Test 4)

### **6.1.1. Administration**

Study interventions will be administered orally and according to the conditions described in the [SoA](#) section and Protocol [Section 5.3.2 Meals and Dietary Restrictions](#).

On Day 1 of each treatment period, following an overnight fast of at least 10 hours, participants will receive nirmatrelvir 300 mg (as 2 × 150 mg tablets) with ritonavir 100 mg (as 1 × 100 mg tablet) commercial tablets or nirmatrelvir/ritonavir 300/100 mg as 2 tablets of nirmatrelvir/ritonavir 150/50 mg FDC tablets Test formulation 1 (low disintegrant), or nirmatrelvir/ritonavir 300/100 mg as 2 tablets of nirmatrelvir/ritonavir 150 mg/50mg FDC tablets Test formulation 2 (high disintegrant), or nirmatrelvir/ritonavir 300 mg/100 mg as 2 tablets of nirmatrelvir/ritonavir 150/50 mg FDC tablets Test formulation 3 (high drug loading) or nirmatrelvir/ritonavir 300/100 mg as 3 tablets of nirmatrelvir/ritonavir 100/33.3 mg FDC tablets Test formulation 4 with approximately 240 mL ambient temperature water administered orally starting at approximately 0800 hours (plus or minus 2 hours). Nirmatrelvir and ritonavir will be dosed simultaneously (within no more than 5 minutes of each other). Participants will swallow all tablet formulations whole and will not manipulate or chew the tablets prior to swallowing.

In order to standardize the conditions on PK sampling days, all participants will be required to refrain from lying down (except when required for BP, PR, and ECG measurements), eating, and drinking beverages other than water during the first 4 hours after nirmatrelvir/ritonavir dosing.

### **6.2. Preparation, Handling, Storage, and Accountability**

1. The investigator or designee must confirm that appropriate conditions (eg, temperature) have been maintained during transit for all study interventions received and any discrepancies are reported and resolved before use of the study intervention.
2. Only participants enrolled in the study may receive study intervention and only authorized site staff may supply, prepare, and/or administer study intervention.
3. All study interventions must be stored in a secure, environmentally controlled, and monitored (manual or automated recording) area in accordance with the labeled storage conditions with access limited to the investigator and authorized site staff. At a minimum, daily minimum and maximum temperatures for all site storage locations must be documented and available upon request. Data for nonworking days must indicate the minimum and maximum temperatures since previously documented for all site storage locations upon return to business.
4. Any excursions from the study intervention label storage conditions should be reported to Pfizer upon discovery along with any actions taken. The site should actively pursue options for returning the study intervention to the labeled storage conditions described in the labeling, as soon as possible. Once an excursion is identified, the study intervention must be quarantined and not used until Pfizer provides permission to use the study intervention. Specific details regarding the

excursion definition and information to report for each excursion will be provided to the site in the PCRU site procedures.

5. Any storage conditions stated in the SRSD will be superseded by the storage conditions stated on the label.
6. Study interventions should be stored in their original containers.
7. The investigator, institution, head of the medical institution (where applicable), or authorized site staff is responsible for study intervention accountability, reconciliation, and record maintenance (ie, receipt, reconciliation, and final disposition records), such as the IPAL or sponsor-approved equivalent. All study interventions will be accounted for using a study intervention accountability form/record.
8. Further guidance and information for the final disposition of unused study interventions are provided in the PCRU's site procedures. All destruction must be adequately documented. If destruction is authorized to take place at the investigator site, the investigator must ensure that the materials are destroyed in compliance with applicable environmental regulations, institutional policy, and any special instructions provided by Pfizer.

Upon identification of a product complaint, notify the sponsor within 1 business day of discovery.

### **6.2.1. Preparation and Dispensing**

Within this protocol, preparation refers to the investigator site activities performed to make the study intervention ready for administration or dispensing to the participant by qualified staff. Dispensing is defined as the provision of study intervention, concomitant treatments, and accompanying information by qualified staff member(s) to a healthcare provider, participant in accordance with this protocol. Local health authority regulations or investigator site guidelines may use alternative terms for these activities.

Nirmatrelvir 150 mg tablets will be prepared at the PCRU in the individual dosing containers by 2 operators, 1 of whom is an appropriately qualified and experienced member of the study staff (eg, physician, nurse, physician's assistant, nurse practitioner, pharmacy assistant/technician, or pharmacist). The tablets will be provided in unit dose containers and labeled in accordance with Pfizer regulations and the clinical site's labeling requirements.

Commercial ritonavir (Norvir® or other local commercialized product) oral tablets will be dispensed at the PCRU into individual dosing containers using the package insert as guidance. All study intervention should be prepared and dispensed by an appropriately qualified and experienced member of the study staff (eg, physician, nurse, physician's assistant, nurse practitioner, pharmacy assistant/technician, or pharmacist) as allowed by local, state, and institutional guidance. A second staff member will verify the dispensing.

Nirmatrelvir/ritonavir FDC tablets will be prepared at the PCRU in the individual dosing containers by 2 operators, 1 of whom is an appropriately qualified and experienced member of the study staff (eg, physician, nurse, physician's assistant, nurse practitioner, pharmacy assistant/technician, or pharmacist). Prepared doses will be provided in unit dose containers and labeled in accordance with Pfizer regulations and the investigator site's labeling requirements.

### **6.3. Assignment to Study Intervention**

The investigator's knowledge of the treatment should not influence the decision to enroll a particular participant or affect the order in which participants are enrolled.

The investigator will assign participant numbers to the participants as they are screened for the study. Pfizer will provide a randomization schedule to the investigator and, in accordance with the randomization numbers, the participant will receive the study treatment regimen assigned to the corresponding randomization number.

### **6.4. Blinding**

This is an open-label study.

### **6.5. Study Intervention Compliance**

When participants are dosed at the site, they will receive study intervention directly from the investigator or designee, under medical supervision. The date and time of each dose administered in the PCRU will be recorded in the source documents and recorded in the CRF. The dose of study intervention and study participant identification will be confirmed at the time of dosing by a member of the study site staff other than the person administering the study intervention. Study site personnel will examine each participant's mouth to ensure that the study intervention was ingested.

### **6.6. Dose Modification**

No dose modification is anticipated.

### **6.7. Continued Access to Study Intervention After the End of the Study**

No study intervention will be provided to study participants at the end of their study participation. It is expected that participants will be treated as required with standard-of-care treatments, as advised by their usual care physician.

### **6.8. Treatment of Overdose**

For this study, any dose of nirmatrelvir greater than 300 mg or ritonavir 100 mg within a 24-hour time period [ $\pm 2$  hours] will be considered an overdose.

There is no specific treatment for an overdose.

In the event of an overdose, the investigator should:

1. Contact the study medical monitor within 24 hours.
2. Closely monitor the participant for any AEs/SAEs and laboratory abnormalities as medically appropriate and at least until the next scheduled follow-up.
3. Document the quantity of the excess dose as well as the duration of the overdose in the CRF.
4. Overdose is reportable to Pfizer Safety **only when associated with an SAE**.
5. Obtain a blood sample for PK analysis within 1 day from the date of the last dose of study intervention if requested by the study medical monitor (determined on a case-by-case basis).

## 6.9. Prior and Concomitant Therapy

Participants will abstain from all concomitant treatments, except for the treatment of adverse events and hormonal contraceptives that meet the requirements of this study in participants who are WOCBP (see [Appendix 4](#)).

Use of prescription or nonprescription drugs and dietary and herbal supplements are prohibited within 7 days or 5 half-lives (whichever is longer) prior to the first dose of study intervention. Limited use of nonprescription medications that are not believed to affect participant safety or the overall results of the study may be permitted on a case-by-case basis following approval by the sponsor. Acetaminophen/paracetamol may be used at doses of  $\leq 1$  g/day.

As nirmatrelvir and ritonavir are both primarily metabolized by CYP3A4, concomitant use of any medications or substances that are strong inducers of CYP3A4 are prohibited within 28 days prior to dosing of study intervention. Additionally, ritonavir and nirmatrelvir are inhibitors of CYP3A4. Therefore, medications highly dependent on CYP3A4 for clearance and for which elevated plasma concentrations may be associated with serious and/or life-threatening events are not permitted during dosing of nirmatrelvir/ritonavir, through 4 days after the last dose of nirmatrelvir/ritonavir.

All concomitant treatments taken during the study must be recorded with indication, daily dose, and start and stop dates of administration. All participants will be questioned about concomitant treatment at each clinic visit.

Treatments taken within 28 days before the first dose of study intervention will be documented as a prior treatment. Treatments taken after the first dose of study intervention will be documented as concomitant treatments.

### **6.9.1. Rescue Medicine**

There is no rescue therapy to reverse the AEs observed with nirmatrelvir or ritonavir; standard medical supportive care must be provided to manage the AEs.

## **7. DISCONTINUATION OF STUDY INTERVENTION AND PARTICIPANT DISCONTINUATION/WITHDRAWAL**

### **7.1. Discontinuation of Study Intervention**

It may be necessary for a participant to permanently discontinue study intervention. Reasons for permanent discontinuation of study intervention include the following.

- AE requiring discontinuation in investigator's view;
- Pregnancy;
- Positive COVID-19 test.

If study intervention is permanently discontinued, the participant will not remain in the study for further evaluation. See the [SoA](#) for data to be collected at the time of discontinuation of study intervention.

#### **7.1.1. ECG Changes**

A participant who meets either bulleted criterion based on the average of triplicate ECG readings will be withdrawn from the study intervention.

- QTcF >500 msec;
- Change from baseline: QTcF >60 msec.

If a clinically significant finding is identified (including, but not limited to, changes from baseline in QTcF after enrollment), the investigator or qualified designee will determine if the participant can continue in the study and if any change in participant management is needed. This review of the ECG printed at the time of collection must be documented. Any new clinically relevant finding should be reported as an AE.

#### **7.1.2. Potential Cases of Acute Kidney Injury**

Abnormal values in SCr concurrent with presence or absence of increase in BUN that meet the criteria below, in the absence of other causes of kidney injury, are considered potential cases of acute kidney injury and should be considered important medical events.

An increase of  $\geq 0.3$  mg/dL (or  $\geq 26.5$   $\mu$ mol/L) in SCr level relative to the participant's own baseline measurement should trigger another assessment of SCr as soon as practically feasible, preferably within 48 hours from awareness.

If the second assessment (after the first observations of  $\geq 0.3$  mg/dL [or  $\geq 26.5$   $\mu\text{mol/L}$ ] in SCr relative to the participant's own baseline measurement) is  $\geq 0.4$  mg/dL (or  $\geq 35.4$   $\mu\text{mol/L}$ ), the participant should be discontinued from the study and adequate, immediate, supportive measures taken to correct apparent acute kidney injury.

Participants should return to the investigator site and be evaluated as soon as possible, preferably within 48 hours from awareness of the second assessment confirming abnormal SCr result. This evaluation should include laboratory tests, detailed history, and physical assessment. In addition to repeating SCr, laboratory tests should include serum BUN, serum creatine kinase, and serum electrolytes (including at a minimum potassium, sodium, phosphate/phosphorus, and calcium), in addition to urinary dipstick, urine microscopic examination, and urinary indices. All cases confirmed on repeat testing as meeting the laboratory criteria for acute kidney injury, with no other cause(s) of laboratory abnormalities identified, should be considered potential cases of drug-induced kidney injury irrespective of availability of all the results of the investigations performed to determine etiology of the abnormal SCr. If  $\geq 2$  healthy participants are noted to have 2 consecutive SCr results of  $\geq 0.3$  mg/dL (or  $\geq 26.5$   $\mu\text{mol/L}$ ), an assessment of whether the finding may be considered an adverse drug reaction should be undertaken.

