- c. Participants will be admitted to the CRU on Day -1. Participants will be discharged on Period 4 Day 4 following the final assessments.
- d. Medical history will include a history of prior illegal drug, alcohol, and tobacco use, as well as blood donation within prior 60 days. Medical history will be recorded at Screening and updated on Period 1 Day -1.
- e. Demographics will include participant race, ethnicity, age, and gender during the Screening visit.
- f. PE will be performed by trained medical personnel at the investigator site at Screening or Period 1 Day -1 only (height and weight must be obtained at Screening to obtain BMI for eligibility criteria). A brief PE may be performed at other designated time points at the discretion of the investigator.
- g. Safety laboratory assessments including urinalysis, hematology, chemistry and coagulation will be performed at Screening, Period 1 Day -1, Period 4 Day 4, and early termination/discontinuation if applicable. All the safety laboratory samples must be collected following at least a 4-hour fast. Additional safety laboratory assessments may be performed at any time at the discretion of the investigator.
- h. For confirmation of postmenopausal (amenorrheic for at least 12 consecutive months) female participants.
- i. Urine drug (mandatory) and alcohol breath test (at discretion of investigator) will be performed at Screening and on Period 1 Day -1. These tests may be performed at any other time at the discretion of the investigator.
- j. HBsAb will be tested if HBsAg and/or HBcAb are positive.
- k. The investigator or his/her designee will discuss with the participant the need to use highly effective contraception consistently and correctly according to contraception guidelines.

PFIZER CONFIDENTIAL

Visit Identifier Abbreviations used in this table may be found in Appendix 10	Screening a	Period 1					Period 2 & 3				Period 4				Follow-Up	Early Termination/ Discontinuation
Days Relative to Day 1	Days -28 to -2	Day -1	1	2	3	4	1	2	3	4	1	2	3	4	28-35 Days b	

1. Single 12-lead ECG readings approximately will be taken at specified time point. All ECG assessments will be made after at least a 5-minute rest in a supine position and prior to any blood draws or vital sign measurements.
- m. This will be done predose of Period 1 Day 1.

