**Table 3. Protocol-Required Safety Laboratory Assessments**

Hematology	Chemistry	Urinalysis	Other
Hemoglobin	BUN and creatinine	Local Dipstick:	

• SARS-CoV-2 RT-PCR

Hematocrit	Glucose (fasted)	pH	

• Urine drug screeningb

RBC count	Calcium	Glucose (qual)	

• Pregnancy test (<math>\beta</math>-hCG)c

MCV	Sodium	Protein (qual)	

• eGFR [CKD-EPI]

MCH	Potassium	Blood (qual)	

• aPTT

MCHC	Chloride	Ketones	

• PT-INR

Platelet count	Total CO 2 (bicarbonate)	Nitrites	

• Fibrinogen

WBC count	AST, ALT	Leukocyte esterase	
Total neutrophils (Abs)	Total bilirubin		At Screening only:
Eosinophils (Abs)	Alkaline phosphatase		

• FSHd

Monocytes (Abs)	Uric acid	Laboratory:	

• HBsAbe

Basophils (Abs)	Albumin	Microscopy and	

• HBsAg

Lymphocytes (Abs)	Total protein	Culture a	

• HBcAb

- a. Only if urine dipstick is positive for blood, protein, nitrites, or leukocyte esterase and culture only if bacteriuria.
- b. The minimum requirement for drug screening includes cocaine, THC, opiates/opioids, benzodiazepines, and amphetamines (others are site and study specific).
- c. Serum or urine  $\beta$ -hCG for female participants of childbearing potential.
- d. For confirmation of postmenopausal status only.
- e. HBsAb will be tested if HBsAg and/or HBcAb are positive.

The investigator must review the laboratory report, document this review, and record any clinically relevant changes occurring during the study in the AE section of the CRF.

Any remaining serum/plasma from samples collected for clinical safety laboratory measurements at baseline and at all times after dose administration may be retained and stored for the duration of the study. **CCI**

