## 10.7. Appendix 7: Kidney Safety: Monitoring Guidelines

### 10.7.1. Laboratory Assessment of Change in Kidney Function and Detection of Kidney Injury

Standard kidney safety monitoring requires assessment of baseline and postbaseline serum creatinine (Scr measurement to estimate glomerular filtration rate [Scr-based eGFR] or creatinine clearance [eCrCl]). Baseline and postbaseline serum Scys makes it feasible to distinguish AKI from other causes of Scr increase. If Scr increase is confirmed after baseline, then reflex measurement of Scys is indicated to estimate the combined Scr-Scys eGFR calculation (for adults only).

Regardless of whether kidney function monitoring tests are required as a routine safety monitoring procedure in the study, if the investigator or sponsor deems it necessary to further assess kidney safety and quantify kidney function, then these test results should be managed and followed per standard of care.

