### **8.3.5. Laboratory Data**

The baseline is defined as measurement taken on Day -1 of Period 1.

Laboratory data will be listed in accordance with the sponsor reporting standards.

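### Protocol 7.1.2 writes two creatinine criteria as absolute values where increases over the participant's own baseline are meant

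*Protocol*

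**What the plan says.** Protocol Section 7.1.2 (Potential Cases of Acute Kidney Injury) contains three creatinine criteria.

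- **Retest.** A rise of at least 0.3 mg/dL (26.5 µmol/L) over the participant's "own baseline measurement should trigger another assessment of SCr as soon as practically feasible". The reference to baseline is explicit.
- **Discontinuation.** The sentence opens "If the second assessment (after the first observations of" and, inside that parenthesis, describes the first rise relative to baseline. After the parenthesis closes, the test is only that the second assessment is at least 0.4 mg/dL (35.4 µmol/L). If so, the participant should be taken off the study.
- **Two-participant signal.** If two or more "healthy participants are noted to have 2 consecutive SCr results of" at least 0.3 mg/dL (26.5 µmol/L), the possibility of an adverse drug reaction should be assessed. The sentence mentions no increase, no baseline and no dosing.

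Creatinine belongs to the chemistry panel ("BUN and creatinine", Protocol Table 3). Footnote g of the Schedule of Activities says that "chemistry and coagulation will be performed at Screening, Period 1 Day -1, Period 4 Day 4", with a further sample at early termination. SAP Section 8.3.5 fixes the reference point for laboratory data: "The baseline is defined as measurement taken on Day -1 of Period 1". Neither Protocol Appendix 7 nor the SAP restates the two later criteria as changes.

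**The concern.** The second assessment is there to separate a confirmed rise from one that has resolved. A test against an absolute 0.4 mg/dL cannot do that, because nearly every adult value lies above it, including one that has returned to baseline. The signal has the same gap: ordinary values satisfy its wording, so taken alone it does not single out participants whose creatinine has risen.

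The neighbouring Section 7.1.1 shows the protocol marking the distinction when it intends it. Its change criterion reads "Change from baseline: QTcF >60 msec", and only its absolute criterion (QTcF above 500 msec) carries no reference to baseline.

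At stake are a needless removal from the study after recovery and an unneeded adverse-drug-reaction assessment. No efficacy or pharmacokinetic definition is involved.

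**Working it through.** **Units.** With the usual conversion factor of 88.4 (an assumption; the documents do not state it), 0.3 × 88.4 = 26.52 and 0.4 × 88.4 = 35.36. These match the printed 26.5 and 35.4 µmol/L, so the figures themselves are consistent.

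**Discontinuation, worked example.** Assume a baseline of 0.80 mg/dL.

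- First value 1.12: rise 1.12 − 0.80 = 0.32, at least 0.3, so a retest is due.
- Repeat 0.80: rise 0.80 − 0.80 = 0.00.
- As written: 0.80 ≥ 0.40, so the criterion is met.
- As an increase: 0.00 < 0.40, so it is not met. The cut-off would be 0.80 + 0.40 = 1.20.

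The two readings disagree for any repeat from 0.40 up to just under 1.20. The written cut-off is too low by 1.20 − 0.40 = 0.80, which is the baseline itself. To fall below the written threshold, this participant's repeat would have to drop to less than half of baseline (0.40/0.80 = 50%). In general, a repeat back at baseline meets the written criterion whenever baseline is at least 0.40.

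**Are baselines of 0.40 or more ordinary?** The documents give no creatinine distribution, so I used the creatinine-only equations in Protocol Section 10.7.2.1. At SCr up to 0.9 (men) or 0.7 (women):

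- Men: eGFR = 142 × (SCr/0.9)^−0.302 × 0.9938^age
- Women: eGFR = 143 × (SCr/0.7)^−0.241 × 0.9938^age

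Above those values the exponent is −1.200. For a man aged 30 at SCr 0.3, 142 × (0.3/0.9)^−0.302 × 0.9938^30 = 164.2. Solving for SCr at an eGFR of 90 at the same age gives 1.13. The ages and the eGFR of 90 are assumptions; Protocol Section 5.1 sets no upper age limit.

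| Sex, age | eGFR at SCr 0.3 | eGFR at SCr 0.4 | SCr at eGFR 90 | Intended cut-off (+0.40) |
|---|---|---|---|---|
| Men, 18 | 176.9 | 162.2 | 1.20 | 1.60 |
| Men, 30 | 164.2 | 150.5 | 1.13 | 1.53 |
| Men, 60 | 136.2 | 124.9 | 0.96 | 1.36 |
| Men, 75 | 124.1 | 113.8 | 0.87 | 1.27 |
| Women, 18 | 156.8 | 146.3 | 0.94 | 1.34 |
| Women, 30 | 145.5 | 135.8 | 0.88 | 1.28 |
| Women, 60 | 120.8 | 112.7 | 0.75 | 1.15 |
| Women, 75 | 110.0 | 102.6 | 0.69 | 1.09 |

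At age 30, a value below 0.4 corresponds to an eGFR above 150.5 (men) or 135.8 (women). A value low enough to miss the signal's 0.3 corresponds to an eGFR above 164.2 or 145.5. Ordinary values therefore exceed both thresholds read as absolute levels.

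**Direction of the error.** If SCr − baseline ≥ 0.4, then SCr ≥ 0.4 + baseline, which is above 0.4. The same holds with 0.3. The written criteria therefore miss no true rise; they only add cases.

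**When it can act.** Footnote g gives a completer two scheduled pre-dose samples and one scheduled post-dose sample, on Day 4 of Period 4, after the last dose. A needless removal during dosing would have to start from an unscheduled test, which footnote g and Protocol Section 8.3.4 allow.

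**The case against.** The best defence is that the section explains itself. It opens by speaking of abnormal values without another cause of kidney injury, defines the 0.3 threshold as an increase, and describes the repeat as confirming an abnormal result. A repeat at baseline confirms nothing. Appendix 7 points the same way: "If Scr increase is confirmed after baseline, then reflex measurement of Scys is indicated". Section 8.3.4 has clinically significant abnormal results repeated until they return to normal or baseline, and Section 8.1 has safety issues discussed with the sponsor before deciding whether a participant continues. The protocol also shortens repeat criteria elsewhere, as in the ECG rules of Section 8.3.3.

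Most of this stands. It settles what was meant and makes a misapplication unlikely. It does not supply the missing words, and the shortened ECG criterion still names baseline for its change.

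Three stronger readings are tempting, and the documents do not support them.

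- *Any ordinary creatinine leads to discontinuation.* No: a second assessment arises only after a first rise of at least 0.3 mg/dL, and the text says the participant should, not must, be discontinued.
- *The Screening and Day -1 values set off the signal before any dose.* The words taken alone allow this, but the sentence closes a paragraph on confirmed cases and asks about a drug reaction, which cannot precede the drug. It is an artefact of reading the sentence in isolation.
- *The signal could halt the study.* It leads only to an assessment, and the stopping rules in Section 7.1.3 do not use it.

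**Conclusion.** The point holds as a drafting error of minor severity. Two operative safety thresholds lack the baseline reference that the first criterion carries. After a qualifying first rise, a repeat that has fully recovered still meets the discontinuation wording, by a margin equal to the participant's own baseline, and ordinary values meet the wording of the signal.

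The conclusion about the wording needs no assumption beyond baselines of at least 0.4 mg/dL, which the protocol's own equations make close to universal in eligible adults. The 0.80 example only illustrates it. No probability of a needless withdrawal can be given from the documents, and none is claimed. The primary pharmacokinetic analysis would be touched only if an unscheduled test during dosing led to such a withdrawal.

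**What to change.** In Protocol Section 7.1.2:

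- Discontinuation: say that the second assessment shows an increase of at least 0.4 mg/dL (35.4 µmol/L) over that participant's own baseline.
- Signal: say that two or more healthy participants each have two consecutive post-dose increases of at least 0.3 mg/dL (26.5 µmol/L) over their own baseline.

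The thresholds do not change. With an assumed baseline of 0.80, discontinuation would then need a repeat of at least 1.20 and the signal two consecutive post-dose values of at least 0.80 + 0.30 = 1.10. A repeat at baseline would trigger nothing, and pre-dose values could not count.

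The cost is a few words in two sentences at the next amendment, with no added procedures, samples or analyses.
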